Endpoints	
Primary Endpoints - Safety:
 
The safety outcome measures for this study are as follows:
 
• Incidence, nature and severity of adverse events (AEs).• Incidence, nature and severity of serious adverse events (SAEs).• Incidence, nature and severity of adverse events of special interest (AESIs).• Incidence, nature and severity of AEs leading to treatment discontinuation.• Changes from baseline in SBP, DBP, heart rate (HR) and respiratory rate.• Changes from baseline in orthostatic measurements of blood pressure (BP) and HR.• Changes from baseline in ECG parameters (HR, PQ, QRS, QT, RR and QTcF, along with information on T and U waves).• Incidence of clinically significant ECG abnormalities.• Hearing assessment.• Incidence of clinically relevant laboratory abnormalities, based on hematology, coagulation, blood chemistry and urinalysis test results:
○ Hematology: hemoglobin concentration, hematocrit level, erythrocytes and platelet counts, leucocytes differential (absolute) counts (neutrophils, eosinophils, lymphocytes, monocytes and basophils)○ Coagulation: international normalized ratio (INR), activated partial thromboplastin time (aPTT) and prothrombin time (PT)○ Blood chemistry: C-reactive protein (CRP test), aspartate aminotransferase (AST), alanine aminotransferase (ALT), gamma-glutamyl-transferase (GGT), total and conjugated bilirubin, alkaline phosphatase (ALP), albumin, creatine phosphokinase (CPK), creatinine, urea, total protein, total cholesterol, triglycerides, glucose, sodium, chloride, calcium, magnesium, phosphate, potassium○ Urinalysis: protein, blood, glucose, leucocytes, nitrites, pH and crystals.• Incidence of value outside of the normal ranges and of clinically relevant blood chemistry test results for electrolytes:
○ Sodium, chloride, calcium, magnesium, phosphate, potassium 
Secondary Endpoints - Pharmacokinetics:
 
• [REDACTED] plasma concentration will be evaluated at Days 1, 7, and 14 to 18.• Plasma concentrations of [REDACTED] and associated PK parameters: Area under the plasma concentration-time curve ($AUC_{0-\tau}$, $AUC_{0-\text{last}}$, $AUC_{0-\infty}$), minimum plasma concentration prior to administration (C_{trough}), maximum plasma concentration (C_{max}, $C_{\text{max,ss}}$), time of
-----------	--

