4.6.1.4 ELECTROCARDIOGRAMS

ECG recordings will be performed as specified in the Schedule of Assessments. Whenever possible, the same brand/model of a standard high-quality, high-fidelity

ECG machine equipped with computer-based interval measurements should be used for each patient. The conditions of the post-dose recordings should be as close as possible to pre-dose time points; this includes but is not limited to food intake, activity level, stressors and room temperature. To minimize variability, the ECG will be recorded in triplicate at baseline (recorded 1 minute apart) and it is important that patients be in a resting position for at least 10 minutes prior to each ECG evaluation. Body position should be consistently maintained for each ECG evaluation to prevent changes in HR. Environmental distractions (e.g., television, radio, conversation) should be avoided during the pre-ECG resting period and during ECG recording. ECGs should be performed prior to meals and any scheduled vital sign measurements and blood draws. In some cases, it may be appropriate to repeat abnormal ECGs to rule out improper lead placement as contributing to the ECG abnormality.

For safety monitoring purposes, the investigator or designee must review, sign and date all ECG tracings. Paper or electronic copies will be kept as part of the patient's permanent study file at the site.

ECG characteristics, including heart rate, QRS duration and HR, and QT intervals will be recorded on the eCRF. QTcF (Fredericia's correction) and RR will be recorded on the eCRF. Changes in T-wave and U-wave morphology and overall ECG interpretation will be documented on the eCRF. T-wave information will be captured as normal or abnormal, U-wave information will be captured in two categories: absent/normal or abnormal.

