11. APPENDIX 1 SCHEDULE OF ASSESSMENTS

PERIOD	SCREENING	TREATMENT PERIOD			FOLLOW-UP VISITS	
		Day 1	Day 7	Day 14	Day 15-18 ^e	Day 28
Visit Window		+/-1	+/-1	+/-1	+/-2	
Assessments						
Informed Consent	x					
Eligibility	x					
Randomization		x				
Demography	x					
Medical History	x					
Physical Examination	x	x	x	x		x
Vital Signs	x	x ^a	x	x ^a		x
Orthostatic BP	x	x ^a	x	x ^a		x
ECG-12 Lead	x	x ^a	x	x ^a		x
Hearing Assessment		x	x	x		x
Serology	x					
Pregnancy Test (urine) ^b	x					x
SARS-CoV-2 Test (nasal swab, saliva)	x					
Substance Abuse (urine test)	x	x				
Blood Chemistry	x		x	x		x
Hematology	x		x	x		x
Coagulation	x		x	x		x
Urinalysis	x		x	x		x
Alcohol (urine test)	x					
Administration of Study Medication ^c		x	x	x		
Study medication supply		x				
Drug Accountability			x	x		x ^f
Blood PK Sample ^d		x	x	x	x	
Urine PK Sample ^d		x		x		
Suicidality (C-SSRS, C-CASA)	x	x	x	x	x	x
ABC-C	x			x		x
SRS-2	x			x		
SB5 ABIQ	x					
OACIS-Severity	x			x		
OACIS-Change				x		
████████	x	x		x		x
KiTAP	x	x		x		x
Eye Tracking		x		x		x
EEG		x		x		x
CSHQ	x	x		x		x
CGI-I				x		x
CGI-S	x			x		x
Adverse Events	x	x	x	x	x	x
Previous and Concomitant Treatments	x	x	x	x	x	x

a To be performed pre-dose and between 4 and 5 hours post-dose as specified in the protocol.

b Females only.

c Patients will receive their AM and PM dose of study drug during the Day 1, Day 7 and Day 14 visits to allow for proper PK sampling.

d PK samples will be collected as described in the PK assessment section. A 5 minutes window for each timepoint is allowed

e Day 16 to Day 18 are optional

f If not done at Day 14 visit

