Summary statistics (n, mean, median, SD, minimum, and maximum) will be computed on the raw and change from baseline values for standard vital sign measurements (temperature and respiratory rate) by visit and time for each treatment. The Day 1 prior to treatment time point will serve as baseline. If there are multiple vital signs taken at any time point, then the latest set of vital signs

will be used for the analysis.

Additionally, summary statistics will be computed on the raw and change from baseline values for the orthostatic vital sign measurements (BP and HR) by visit and time for each treatment. The Day 1 prior to treatment time point will serve as baseline. Spaghetti plots of the raw values for orthostatic diastolic BP, orthostatic systolic BP and orthostatic HR will be displayed by patient, time point and treatment.

All vital signs will be provided in data listings as shown in Appendix B. Vital signs taken while standing will be included in the data listings but will not be summarized in the tables.

Physical Examination

All physical examination results will be listed as shown in Appendix B.

ECG

The ECG parameters of interest include HR, PQ, QRS, QT, RR, and QTcF along with information on T and U waves.

As the ECGs are performed in triplicate at Day 1 prior to treatment, the average of the three values for each of the ECG parameters will be used as the baseline value. Summary statistics (n, mean, median, SD, minimum, and maximum) will be computed on the raw and change from baseline values for each parameter by visit and time by treatment and overall. The Day 1 prior to treatment time point will serve as baseline. Spaghetti plots of the raw values for HR and QTcF will be displayed by patient, time point and treatment.

The ECG Interpretations for each of the three ECGs on Day 1 prior to treatment will be used to obtain a Combined Overall ECG Interpretation. The Combined Overall ECG Interpretation in relation to clinical significance at Day 1 prior to treatment (i.e., baseline) will be determined as follows:

- If at least one ECG Interpretation = 'Abnormal – clinically significant', then the Combined Overall ECG Interpretation = 'Abnormal – clinically significant'.
- Else if there are no readings such that ECG Interpretation = 'Abnormal – clinically significant' and there is at least one ECG Interpretation = 'Abnormal – not clinically significant', then the Combined Overall ECG Interpretation = 'Abnormal – not clinically significant'.

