- Else if there are no readings such that ECG Interpretation = 'Abnormal – clinically significant' or "Abnormal – not clinically significant" and there is at least one ECG Interpretation = 'Normal', then the Combined Overall ECG Interpretation = 'Normal'.
- Else if all readings have a missing result for ECG Interpretation then the Combined Overall ECG Interpretation is missing.

Additionally, results from the ECG findings will be determined for T wave, U wave, and ECG Interpretation regardless of clinical significance. The Combined Overall T wave, U wave, and ECG Interpretation at Day 1 prior to treatment (i.e. baseline) will be determined by parameter as follows:

- If at least one ECG finding = 'Abnormal', then the Combined Overall finding = 'Abnormal'.
- Else if there are no readings such that ECG finding = 'Abnormal' and there is at least one ECG finding = 'Normal', then the Combined Overall finding = 'Normal'.
- Else if all readings have a missing result for ECG finding then the Combined Overall finding is missing.

Shift tables will be constructed to show the changes in ECG findings in relation to clinical significance (e.g., normal, abnormal clinically significant (CS), abnormal not clinically significant (NCS)) and findings (e.g., normal, abnormal) by parameter from baseline to each visit by treatment and overall.

All ECG data will be provided in data listings as shown in Appendix B.

Laboratory Results

The laboratory tests of interest include blood chemistry, serology, hematology, coagulation, and urinalysis results.

Summary statistics (n, mean, median, SD, minimum, and maximum) will be computed on the raw and change from baseline values for each quantitative laboratory parameter by visit for each treatment group and overall. The screening time point will serve as baseline.

Spaghetti plots of the raw values for sodium, chloride, calcium, magnesium, phosphate, potassium, and platelet count will be displayed by patient, time point and treatment.

For those urinalysis parameters that are qualitative in nature, the number and proportion of patients with each result for each parameter will be summarized by visit and treatment.

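### The categorical ECG baseline is the worst of three tracings while later time points appear to be single tracings, which tilts shift Tables 18–19 toward fewer new abnormalities and more apparent improvement

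*SAP*

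**What the plan says.** Protocol 4.6.1.4 states that "the ECG will be recorded in triplicate at baseline (recorded 1 minute apart"; it asks for triplicates at no other time. Appendix 1 schedules ECGs at screening and on Days 1, 7, 14 and 28, with a note for Days 1 and 14: "To be performed pre-dose and between 4 and 5 hours post-dose as specified in the protocol".

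SAP 4.2 treats the three baseline tracings in two ways:

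- **Numeric parameters** (HR, PQ, QRS, QT, RR, QTcF): "the average of the three values for each of the ECG parameters will be used as the baseline value".
- **Categorical results:** "The ECG Interpretations for each of the three ECGs on Day 1 prior to treatment will be used to obtain a Combined Overall ECG Interpretation", with CS taking precedence over NCS, and NCS over normal. For T wave, U wave and interpretation regardless of significance, the rule is "If at least one ECG finding = 'Abnormal', then the Combined Overall finding = 'Abnormal".

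The shift tables then run "from baseline to each visit by treatment and overall". Table 18 uses three categories (normal, NCS, CS). Table 19 uses two (normal, abnormal) for T wave, U wave and interpretation. The SAP gives no combining rule for any later time point. The Table 17 shell has a time column, but the shells of Tables 18 and 19 do not.

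The protocol synopsis lists, among the primary safety endpoints, "Incidence of clinically significant ECG abnormalities".

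**The concern.** A worst-of-three baseline has three chances to be called abnormal, while a later time point appears to have one. A patient with a single stray abnormal reading among the three is filed as abnormal at baseline. In Table 19 that patient can no longer appear as newly abnormal, and a normal tracing later appears as an improvement. In Table 18 the same happens to a new NCS finding.

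The direction is fixed. Every patient who is abnormal on one chosen baseline tracing is also abnormal on worst-of-three, so the rule can only move patients out of the normal baseline group. In a first-in-human combination study with safety as its primary objective, that is the less cautious direction.

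The reporting around it adds to the concern. Tables 17–19 are the only planned ECG tables. Electrolytes get a count of patients outside the normal range whatever the baseline (Table 31), but ECG has no such count, although its endpoint is worded as an incidence.

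**Working it through.** The documents state no figure for these tables, so there is none to reproduce.

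**Inputs from the documents.** Three baseline tracings, any one of which makes baseline abnormal (SAP 4.2). One tracing per later time point, which is inferred because triplicates are specified only at baseline. Up to 6 patients per active dose and at most 4 on placebo (Protocol 6.1).

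**Assumed inputs.** The probability p that a tracing is read abnormal, and the correlation ρ between tracings of one patient. Neither is in the documents. I take p = 0.10 as the worked case and ρ from 0 to 0.9, with no drug effect.

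**Independent tracings (ρ = 0).**

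- Baseline abnormal: 1 − (1 − p)³ = 1 − 0.729 = 27.1%, against 10% for one tracing.
- Normal-to-Abnormal: p(1 − p)³ = 0.10 × 0.729 = 7.3%.
- Abnormal-to-Normal: (1 − p)[1 − (1 − p)³] = 0.90 × 0.271 = 24.4%.
- One tracing against one: p(1 − p) = 9.0% in each direction, net zero.

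**Correlated tracings.** These use a beta-binomial with mean p and intraclass correlation ρ. Put s = (1 − ρ)/ρ and b = (1 − p)s. The chance that all three are normal is b(b + 1)(b + 2) / [s(s + 1)(s + 2)]. At ρ = 0.9, s = 0.111 and b = 0.1, which gives 0.231/0.2606 = 0.886, so baseline is abnormal in 11.4%. One against one is p(1 − p)(1 − ρ) in each direction.

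| ρ | Baseline abnormal, SAP rule | Normal-to-Abnormal, SAP rule | Abnormal-to-Normal, SAP rule | Each direction, one v one | Net, SAP rule |
|---|---|---|---|---|---|
| 0 | 27.1% | 7.3% | 24.4% | 9.0% | −17.1 points |
| 0.3 | 20.8% | 3.5% | 14.3% | 6.3% | −10.8 points |
| 0.6 | 15.8% | 1.5% | 7.3% | 3.6% | −5.8 points |
| 0.9 | 11.4% | 0.3% | 1.7% | 0.9% | −1.4 points |

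The net shift equals the chance of an abnormal visit minus the chance of an abnormal baseline. It therefore depends only on how well the three baseline tracings agree with each other, and it is zero if they always agree.

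**Other rates.** For p = 0.05, 0.20 and 0.30 the net is −9.3, −28.8 and −35.7 points at ρ = 0, and −0.7, −2.4 and −3.2 points at ρ = 0.9.

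**In six patients, p = 0.10.** Expected Abnormal-to-Normal shifts are 1.46 against 0.54 at ρ = 0, and 0.10 against 0.05 at ρ = 0.9.

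**With a real effect.** If the drug made all six abnormal, the number shown as Normal-to-Abnormal would be 6 × the chance of a normal baseline. That is 6 × 0.729 = 4.4 at ρ = 0 and 6 × 0.886 = 5.3 at ρ = 0.9, against 6 × 0.90 = 5.4 with one baseline tracing.

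**Day 14.** If the two Day 14 ECGs were also combined as worst of two, the visit would be abnormal in 1 − 0.81 = 19%. The net would be 19 − 27.1 = −8.1 points at ρ = 0. The SAP does not say which Day 14 tracing enters the tables. SAP 1.2 marks the Day 1 ECG as pre- and post-dose but does not mark the Day 14 ECG.

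**The case against.** The case for leaving the rule alone has real strength.

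- **The rule is a coherent definition.** Calling a finding new only if it was absent from all three pre-dose tracings is a recognisable treatment-emergent rule. A single baseline tracing can miss an intermittent pre-existing abnormality and then count it as new. This stands, and it is why worst-of-three should be kept as a supplement.
- **Clinically significant findings are not hidden.** A reader might infer that the rule conceals new CS abnormalities. It does not: after an NCS baseline they appear in Table 18 as NCS-to-CS. Only a CS baseline could mask them, and exclusion criterion 13 should make that rare.
- **Per-visit totals can be recovered.** Tables 18–19 divide by all Safety patients in the group, so adding the cells with an abnormal visit result gives the proportion abnormal at that visit. This stands. A per-patient count of any post-dose abnormality cannot be obtained from the tables, although Listing 6 allows it by hand.
- **The size may be small.** Tracings one minute apart at rest may agree closely, and the bias then nearly vanishes.
- **Other safeguards exist.** Numeric changes use the mean of three, HR and QTcF are plotted by patient, and Listing 5 keeps every baseline tracing. The analysis is descriptive, and the same rule applies to placebo. With at most 4 placebo patients, however, placebo is a weak guide to how far the active counts are off.

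Two further inferences go too far. One is that every later visit has one tracing: Appendix 1 gives Day 14 two time points. The other is to read 7.3% against 9.0% as a share of drug-related findings lost: under no drug effect, those shifts are all chance.

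**Conclusion.** The asymmetry is in the text and its direction follows from the rule. Unless the three baseline tracings always agree, the shift tables show too few Normal-to-Abnormal and too many Abnormal-to-Normal changes relative to a like-for-like comparison. The effect falls mainly on Table 19 and on the Normal-to-NCS cells of Table 18.

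The size is not known from the documents. With an assumed 10% rate per tracing and no drug effect, it lies between −17 points and about −1.4 points as the correlation goes from 0 to 0.9, and reaches zero with perfect agreement. This also rests on the inference of one tracing per later time point.

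A reader might conclude that the primary ECG analysis is invalid. The SAP does not label these tables primary, and no data are lost. This is a cheap improvement, not a must-fix.

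**What to change.** In SAP 4.2, before unblinding:

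1. Base Tables 18–19 on one pre-specified pre-dose tracing, so that baseline and each post-dose time point rest on one reading. A two-of-three majority is closer than worst-of-three but not neutral: at p = 0.10 its net is +7.2 points at ρ = 0 and +0.7 at ρ = 0.6.
2. Show Day 14 pre-dose and post-dose separately, and state which tracing counts when an abnormal ECG is repeated, as Protocol 4.6.1.4 allows.
3. Keep worst-of-three as a supplementary count of abnormalities absent from all three baseline tracings, with all three tracings in Listing 5.
4. Add, by treatment, the number of patients with any post-dose abnormal ECG and with any post-dose CS ECG, whatever the baseline. This reports the stated incidence endpoint.

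Keep the mean of three for numeric parameters.

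The cost is one SAP paragraph, table footnotes and some reprogramming, with no new data. The downside is that one baseline tracing can miss an intermittent pre-existing abnormality; item 3 covers that.

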3.3 OUTCOME MEASURES

3.3.1 SAFETY OUTCOME MEASURES

The safety outcome measures for this study are as follows:

- Incidence, nature and severity of AEs.
- Incidence, nature and severity of SAEs.
- Incidence, nature and severity of AESIs.
- Incidence, nature and severity of AEs leading to treatment discontinuations.
- Changes from baseline in systolic blood pressure (SBP), diastolic blood pressure (DBP), heart rate (HR) and respiratory rate.
- Changes from baseline in orthostatic measurements of BP and HR.
- Changes from baseline in ECG parameters (HR, PQ, QRS, QT, RR and QTcF, along with information on T and U waves).
- Incidence of clinically significant ECG abnormalities.
- Hearing assessment
- Incidence of clinically relevant laboratory abnormalities, based on hematology, blood chemistry and urinalysis test results:
 - Hematology: hemoglobin, hematocrit, erythrocytes, platelet count, leucocytes differential (absolute) counts (neutrophils, eosinophils, lymphocytes, monocytes, basophils).
 - Blood chemistry: aspartate aminotransferase (AST), alanine aminotransferase (ALT), gamma-glutamyltransferase (GGT), total and conjugated bilirubin, alkaline phosphatase (ALP), albumin, creatine phosphokinase (CPK), creatinine, urea, total protein, total cholesterol, triglycerides, sodium, chloride, calcium, magnesium, phosphate, potassium, glucose.
- Incidence of value outside of the normal ranges of blood chemistry test results for electrolytes:
 - Sodium, chloride, calcium, magnesium, phosphate, potassium
- Urinalysis: protein, blood, glucose, leucocytes, nitrites, pH, and presence of crystals.

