4.6.1.5 LABORATORY ASSESSMENTS

Normal ranges for the study laboratory parameters must be supplied to the sponsor before the study starts. Laboratory safety tests shall be collected at time-points specified in the Schedule of Assessments ([Appendix 1](#)).

Additional blood or urine samples may be taken at the discretion of the investigator if the results of any test fall outside the reference ranges, or clinical symptoms necessitate additional testing to monitor patient's safety. Where the clinical significance of abnormal laboratory results is considered uncertain, screening laboratory tests may be repeated before randomization to confirm eligibility. If there is an alternative explanation for a positive urine or blood test for drugs of abuse, e.g., previous occasional intake of a medication or food-containing for example, codeine, benzodiazepines or opiates, the test could be repeated to confirm washout.

In the event of unexplained abnormal clinically significant laboratory test values, the tests should be repeated immediately and followed up until they have returned to the normal range and/or an adequate explanation of the abnormality is found. Results of clinical laboratory testing will be recorded on the eCRF or be received as electronically produced laboratory reports submitted directly from the local or central laboratory.

When a fasted state is required, subjects have to be fasted for at least 4 hours.

Blood samples for the following laboratory tests will be sent to the local laboratory(ies) for analysis.

- Hematology (5 mL per sample): hemoglobin, hematocrit, erythrocytes, platelet count, leucocytes differential (absolute) counts (neutrophils, eosinophils, lymphocytes, monocytes, basophils).

- Blood chemistry (5 mL per sample): C-reactive protein (CRP test), AST, ALT, GGT, total and conjugated bilirubin, alkaline phosphatase (ALP), lactate, pyruvate, albumin, creatine phosphokinase (CPK), creatinine, urea, total protein, total cholesterol, triglycerides, sodium, chloride, calcium, magnesium, phosphate, potassium, glucose.
- Coagulation (2 mL per sample): international normalized ratio (INR), activated partial thromboplastin time (aPTT), prothrombin test (PT).
- Viral serology (2 mL per sample):
 - HIV (specific tests HIV-1 antibody).
 - Hepatitis B surface antigen (HBsAg).
 - Total hepatitis B core antibody (HBcAb).
 - Hepatitis C virus (HCV) antibody.

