5.1.3 ADVERSE EVENTS OF SPECIAL INTEREST (IMMEDIATELY REPORTABLE TO THE SPONSOR)

AESIs are required to be reported by the investigator to the sponsor immediately (i.e., no more than 24 hours after learning of the event; see [Section 5.4.2](#) for reporting instructions). AESIs for this study include the following:

- Electrolyte imbalance: hypokalemia (K⁺ level <3.4 mEq/L), hyperkalemia (>5.0 mEq/L), hyponatremia (Na⁺ level <135 mEq/L), hypochloremia (Cl⁻ level <97 mEq/L)
- Thrombocytopenia is defined as meeting one or both criteria:
 - Platelet count below $150 \times 10^9/L$ (or 150.000 platelets per microliter (mcL))
 - Platelet count drop of $\geq 50\%$ compared to baseline
- Drug-induced liver injury (DILI)
- Dehydration and orthostasis (defined by a fall in systolic blood pressure over 20 mm Hg or a fall in diastolic pressure over 10 mm Hg within 3 minutes of standing).

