5.3.5.4 ABNORMAL LABORATORY VALUES

Not every laboratory abnormality qualifies as an AE. A laboratory test result should be reported as an AE if it meets any of the following criteria:

- Accompanied by clinical symptoms.
- Results in a change in study treatment (e.g., dosage modification, treatment interruption, or treatment discontinuation).
- Results in a medical intervention (e.g., potassium supplementation for hypokalemia) or a change in concomitant therapy.
- Clinically significant in the investigator's judgment.

It is the investigator's responsibility to review all laboratory findings. Medical and scientific judgment should be exercised in deciding whether an isolated laboratory abnormality should be classified as an AE.

If a clinically significant laboratory abnormality is a sign of a disease or syndrome (e.g., ALP and bilirubin 5 times the upper limit of normal (ULN) associated with cholecystitis), only the diagnosis (i.e., cholecystitis) should be recorded on the AE eCRF page.

If a clinically significant laboratory abnormality is not a sign of a disease or syndrome, the abnormality itself should be recorded on the AE eCRF page, along with a descriptor indicating if the test result is above or below the normal range (e.g., "elevated potassium", as opposed to "abnormal potassium"). If the laboratory abnormality can be characterized by a precise clinical term per standard definitions, the clinical term should be recorded as the AE. For example, a serum potassium level of 7.0 mEq/L should be recorded as "hyperkalemia".

Observations of the same clinically significant laboratory abnormality from visit to visit should not be repeatedly recorded on the AE eCRF page, unless the etiology changes. The initial severity of the event should be recorded, and the severity or seriousness should be updated any time the event worsens.

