Shift tables will be constructed to show the changes in laboratory results in relation to clinical significance (e.g., normal, abnormal clinically significant (CS), abnormal not clinically significant (NCS)) from baseline to each visit. This analysis will be repeated for blood chemistry results for electrolytes (sodium, chloride, calcium, magnesium, phosphate, potassium).

A shift table for blood chemistry results for electrolytes will be constructed to show the changes in laboratory results in relation to range of normal results (e.g., normal, high, low) from baseline to each visit.

The count and proportion of patients with blood chemistry results for electrolytes outside of the normal range (low, high) for each visit will be summarized by treatment and overall.

All laboratory results data will be provided in data listings as shown in Appendix B.

Hearing Assessment

The patient responses to the hearing assessment for each visit will be listed as shown in Appendix B.

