STP1- X ^{mg} ibudilast	xxxxxx	xxx (xx)	xxx (xx)	xxx (xx)	xxx (xx)	xxx (xx)	xxx (xx)	xxx (xx)	xxx (xx)	xxx (xx)
Placebo	xxxxxx	xxx (xx)	xxx (xx)	xxx (xx)	xxx (xx)	xxx (xx)	xxx (xx)	xxx (xx)	xxx (xx)	xxx (xx)
Overall	xxxxxx	xxx (xx)	xxx (xx)	xxx (xx)	xxx (xx)	xxx (xx)	xxx (xx)	xxx (xx)	xxx (xx)	xxx (xx)
xxxxxx	xxx (xx)	xxx (xx)	xxx (xx)	xxx (xx)	xxx (xx)	xxx (xx)	xxx (xx)	xxx (xx)	xxx (xx)	xxx (xx)
xxxxxx	xxx (xx)	xxx (xx)	xxx (xx)	xxx (xx)	xxx (xx)	xxx (xx)	xxx (xx)	xxx (xx)	xxx (xx)	xxx (xx)
xxxxxx	xxx (xx)	xxx (xx)	xxx (xx)	xxx (xx)	xxx (xx)	xxx (xx)	xxx (xx)	xxx (xx)	xxx (xx)	xxx (xx)
xxxxxx	xxx (xx)	xxx (xx)	xxx (xx)	xxx (xx)	xxx (xx)	xxx (xx)	xxx (xx)	xxx (xx)	xxx (xx)	xxx (xx)
xxxxxx	xxx (xx)	xxx (xx)	xxx (xx)	xxx (xx)	xxx (xx)	xxx (xx)	xxx (xx)	xxx (xx)	xxx (xx)	xxx (xx)
xxxxxx	xxx (xx)	xxx (xx)	xxx (xx)	xxx (xx)	xxx (xx)	xxx (xx)	xxx (xx)	xxx (xx)	xxx (xx)	xxx (xx)

^a normal result are those results that the Principal Investigator determined to be within normal range.

^b The denominator for all proportions is the number of Safety population patients in the corresponding treatment group and overall.
 STATKING Clinical Services (month day, year)
 Source Program: xxxxxx.sas

Laboratory parameters include: sodium, chloride, calcium, magnesium, phosphate, and potassium.

Statistical Analysis Plan

STP1-C004

Table 31. Number and Proportion of Patients with Blood Chemistry Results for Electrolytes Outside of Normal Range
STATICLA SA – Study No. STP1-C004
Safety Population (N=xxxx)

Parameter (units)	Visit	Result	STP1-  mg ibudilast (N=xxx) ^a	STP1-  mg ibudilast (N=xxx) ^a	Placebo (N=xxx) ^a	Overall (N=xxx) ^a
xxxxxx (xxx)	xxxxxx	Low	xxx (xxx)	xxx (xxx)	xxx (xxx)	xxx (xxx)
		High	xxx (xxx)	xxx (xxx)	xxx (xxx)	xxx (xxx)
xxxxxx	xxxxxx	Low	xxx (xxx)	xxx (xxx)	xxx (xxx)	xxx (xxx)
		High	xxx (xxx)	xxx (xxx)	xxx (xxx)	xxx (xxx)
xxxxxx (xxx)	xxxxxx	Low	xxx (xxx)	xxx (xxx)	xxx (xxx)	xxx (xxx)
		High	xxx (xxx)	xxx (xxx)	xxx (xxx)	xxx (xxx)
xxxxxx (xxx)	xxxxxx	Low	xxx (xxx)	xxx (xxx)	xxx (xxx)	xxx (xxx)
		High	xxx (xxx)	xxx (xxx)	xxx (xxx)	xxx (xxx)
xxxxxx	xxxxxx	Low	xxx (xxx)	xxx (xxx)	xxx (xxx)	xxx (xxx)
		High	xxx (xxx)	xxx (xxx)	xxx (xxx)	xxx (xxx)

The denominator for all proportions is the number of Safety population patients in the corresponding treatment group and overall.
STATKING Clinical Services (DDMMYY)
Source Program: xxxxxxx.sas

Laboratory parameters include: sodium, chloride, calcium, magnesium, phosphate, and potassium.

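### SAP Table 31 reports out-of-range electrolytes only visit by visit, over all Safety patients, so for most electrolytes no table prints how many patients were ever out of range after dosing

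*SAP*

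**What the plan says.** **The outcome.** Protocol 3.3.1 lists "Incidence of value outside of the normal ranges of blood chemistry test results for electrolytes" and names sodium, chloride, calcium, magnesium, phosphate and potassium. The synopsis puts the outcome under the primary safety endpoints, as "Incidence of value outside of the normal ranges and of clinically relevant blood chemistry test results for electrolytes". Neither place defines incidence as per patient or on treatment.

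**The analysis.** SAP 4.2 specifies: "The count and proportion of patients with blood chemistry results for electrolytes outside of the normal range (low, high) for each visit". The Table 31 shell has rows for parameter, visit and low or high, and none that combines visits. Its footnote reads: "The denominator for all proportions is the number of Safety population patients in the corresponding treatment group and overall". SAP 2.3 says that analyses rest on observed data, with no imputation.

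**Sampling.** Chemistry is drawn at screening (the SAP's laboratory baseline) and on Days 7, 14 and 28. Protocol 4.6.1.5 adds: "Additional blood or urine samples may be taken at the discretion of the investigator if the results of any test fall outside" the reference ranges. For vital signs SAP 4.2 has a repeat rule ("If there are multiple vital signs taken at any time point, then the latest set of vital signs" is used). It has none for laboratory values.

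**Neighbouring outputs.** Protocol 5.1.3 defines electrolyte AESIs for low potassium, high potassium, low sodium and low chloride, and Table 11 counts patients with an AESI. Otherwise, Protocol 5.3.5.4 warns: "Not every laboratory abnormality qualifies as an AE". The value must come with symptoms, change study treatment, lead to an intervention or a change in concomitant therapy, or be judged clinically significant.

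**The concern.** For adverse events, serious adverse events and AESIs, SAP 4.2 counts patients with at least one event. The electrolyte outcome sits in the same protocol list and is also called an incidence, yet its table stops at visit counts. A reader who wants to know how many patients on a dose ever had a low magnesium, say, cannot get that from Table 31, because it does not show whether the patients low on Day 7 are the same as those low on Day 14.

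Two details blur the visit counts themselves. A patient with no sample at a visit stays in the denominator and so is treated as in range, which does not sit well with SAP 2.3. And when a low value is repeated, nothing says which result enters the visit row. What is at stake is the printing of a listed primary safety outcome, not the detection of a hazard.

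**Working it through.** The plan gives no figure for this outcome, so there is none to reproduce. Its enrolment figure does show that missing samples are foreseen: 16 / (1 − 0.20) = 20, as SAP 1.3 states.

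**1. Coverage by Table 11**

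- Electrolyte-by-direction combinations: 6 × 2 = 12.
- Defined as AESIs (Protocol 5.1.3): low K+, high K+, low Na+, low Cl− = 4.
- Not defined: 12 − 4 = 8, namely high Na+, high Cl−, and low and high calcium, magnesium and phosphate (1 + 1 + 2 + 2 + 2 = 8).

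In the 4 covered combinations, Table 11 uses the AESI cut-offs rather than the laboratory's range. It also follows the AE reporting period, which runs to the follow-up visit (Protocol 5.3.1), so it is not a count through Day 14.

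**2. What the visit counts determine**

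Let a and b be the numbers low on Day 7 and Day 14 among n patients. From scheduled samples alone, the number ever low lies between max(a, b) and min(n, a + b).

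| n | a, b | Patients ever low | Proportion |
|---|---|---|---|
| 6 | 1, 0 | 1 | 17% (exact) |
| 6 | 1, 1 | 1 to 2 | 17% to 33% |
| 6 | 2, 2 | 2 to 4 | 33% to 67% |
| 3 | 1, 1 | 1 to 2 | 33% to 67% |

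Here n = 6 is the planned maximum on active treatment per dose (Protocol 6.1), and n = 3 is the minimum to be exposed to the highest dose (synopsis). The two limits coincide when either count is 0, or trivially when either count equals n. Otherwise the number is not fixed. Low values found only in unscheduled samples could raise it further.

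**3. Denominator**

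If one of 6 patients has no Day 14 sample and one of the 5 sampled is low, Table 31 prints 1/6 = 17%. The observed-data proportion is 1/5 = 20%.

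**4. What cannot be sized**

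The documents do not give the laboratory's lower limit for potassium, so the gap between that limit and the AESI cut-off of 3.4 mEq/L is unknown. Nor do they give a supplement effect, so any shift in Day 14 potassium is unknown too.

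**The case against.** The strongest reply is that the SAP does what the protocol asks. Protocol 6.4.2 calls for summary statistics at each assessment time and for listings that flag values outside the normal range. Tables 20, 30 and 31 and Listing 7 deliver this. A reader might infer that the SAP departs from a per-patient, on-treatment definition in the protocol. The documents do not support that, because no such definition is there.

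Other outputs also narrow the gap. Table 20 prints n by visit, so the number sampled can be found, and it gives the minimum potassium at each visit. Table 30 shows shifts from baseline and so separates new abnormalities from those already present at screening. The two imbalances given as examples for the diuretic in Protocol 5.2.1.1, hypochloremia and hypokalemia, are among the four combinations that Table 11 covers. With two scheduled on-treatment draws, 6 patients give at most 12 scheduled values per electrolyte, all listed and plotted.

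A second tempting reading is that potassium supplements hide hypokalemia. Supplements are to be given when hypokalemia is seen, so a normal Day 14 value after a low Day 7 value may have been taken on potassium, and Table 31 and Listing 7 do not mark it. But potassium below 3.4 mEq/L is an AESI, and a low value that leads to supplementation is reportable as an AE. Listing 3 dates the event, Listing 32 dates the supplement, and Table 50 counts patients by medication. The low value is recorded; only the cross-reference is missing.

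All of this stands. It lowers the importance of the point but does not supply the missing count: Tables 20, 30 and 31 are all by visit, and none can be added up to patients ever out of range.

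**Conclusion.** The point holds as a minor gap in tabulation. For 8 of 12 electrolyte-by-direction combinations, no table gives the number of patients out of range at any time after dosing, unless the value was also reported as an AE. Visit counts settle that number only in the special cases shown above. The denominator is at odds with SAP 2.3, and a rule for repeat laboratory values is missing.

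This rests on reading incidence as patients with at least one out-of-range value. That is the usual reading, and the one the SAP applies to adverse events, but the protocol does not state it. The 8 of 12 counts every combination equally and does not measure lost safety information. No safety signal is lost, and the count can be made by hand from Listing 7 and Figures 6 to 11.

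**What to change.** In SAP 4.2 and the Table 31 shell:

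1. For each electrolyte, add the number and proportion of patients with any low value, and with any high value, after first dose through the Day 14 visit, scheduled or unscheduled.
2. Show separately the patients who were within range at screening, so that a pre-existing abnormality is not counted as new.
3. Use patients with at least one sample in that window as the denominator for the any-time rows, and patients sampled at the visit for the by-visit rows.
4. State which laboratory value the by-visit rows use when a visit has more than one.

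Optionally, flag in Listing 7 and Figure 11 the potassium values taken between the supplement start and stop dates in Listing 32. This adds little, since Listings 3 and 32 and Table 50 already hold most of it, and it would not capture advice to eat potassium-rich food.

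The cost is a few derived rows from data already collected. Sample size, visits and data collection do not change. The rows for low and high potassium, low sodium and low chloride will partly overlap Table 11. SAP Appendix A says that changes to table format after approval carry a programming charge, so the cost is small but not nil.
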